
To assess the ability of pediatric participants to perform a battery of lab-based tasks.	
Number of participants (overall and per age group) able to perform each of the 7 tasks and task-completion percentage (among total of 7 tasks) per participant.

To assess the compliance in wearing the ActiGraph devices at home.	
Number of hours per day wearing the device and number of days with more than 10 hours of wearing time for each participant.

To evaluate the participant's or caregiver's perception of wearability and comfort of ActiGraph and APDM devices during in-lab sessions.	
In-lab ActiGraph/APDM wearability/comfort questionnaire responses from Visit 1 (Day 1).

 To evaluate the participant's or caregiver's perception of wearability and comfort of ActiGraph devices during the at-home monitoring period. 	
 At-home ActiGraph wearability/comfort questionnaire responses from at-home monitoring period in the Final Study Evaluation (Day 15 + 3 days).

 To evaluate the effect of floor surface (carpet vs tile) on gait metrics collected using ActiGraph and APDM devices. 	
 Gait metrics defined in the Annex 2 (eg, gait speed, stride length) measured by ActiGraph and APDM devices across different floor surfaces.
Tertiary/Exploratory Objective(s):	Tertiary/Exploratory Endpoint(s):

 To investigate the feasibility of using a daily activity diary to provide context in pediatric physical activity data collected by ActiGraph devices at home in pediatric participants. 	
 Daily activity diary responses and metrics related to physical activity endpoints from ActiGraph (eg, sedentary time as defined in Annex 3).

 To compare gait speed collected using the SIMI system and GAITRite® walkway, during in-lab sessions. 	
 Gait speed defined in the Annex 2 measured by SIMI system and GAITRite® walkway.

COHORT B: Panoramic Bracelet Device

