This is a non-randomized, single site, low-interventional study to compare gait and activity quality metrics collected using wearable devices, APDM devices and GAITRite® walkway, during in-lab sessions (in the PfIRe Lab). There will be approximately 39 participants in Cohort A and 39 participants in Cohort B divided equally into 3 independent age groups based on the schematic detailed below:

- Group 1: 3 years to 5 years old inclusive
- Group 2: 6 years to 11 years old inclusive
- Group 3: 12 years to 17 years old inclusive

Participant's assignment to a group will be determined by the age at the time the informed consent is signed. Participants will be recruited into age groups in parallel. Recruitment will stop in a group when there are at least 13 completers in that group. Participants who drop out for reasons other than safety before completion of the study may be replaced.

The study is composed of:

1. A visit at the PfiRe Lab (Visit 1, Day 1), during which participant eligibility will be confirmed, consent and assent will be obtained. Participants will perform in-lab gait and activities monitoring procedures (see [Table 1](#) below). During all these activities, participants will wear or interact with the following devices:

- a. Wearable devices (ActiGraph for Cohort A), (Panoramic Bracelet device and GENEActiv for Cohort B)
- b. GAITRite® Electronic Walkway
- c. Ambulatory Parkinson's Disease Monitoring System (APDM);
- d. Camera based SIMI system

GAITRite® walkway, APDM will be used as reference comparators for the in-lab portion of the protocol. For Cohort B of the protocol the aim is to use GENEActiv as a comparator device to Panoramic Bracelet during the at-home collection period. The in-lab gait and activity monitoring will be video recorded from multiple angles with multiple cameras (camera-basedSIMI system) , this will be used to provide contextual information of each portion of the tasks and procedures that may be used by the reviewer when analyzing and interpreting the sensor data. As a tertiary/exploratory objective, gait speed recorded by the SIMI system against the gait speed collected by GAITRite® walkway may be validated.

Table 1. In-lab Assessments

Assessments	Objectives	Location

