Walking on GAITRite® walkway (20 feet x 3) at participant's natural speed and at various speed	
• Compare gait metrics collected between devices and APDM devices.• Compare gait metrics collected between devices and GAITRite® walkway.• Compare gait speed collected between SIMI system and GAITRite® walkway.	GAITRite® walkway
Walking on tile and carpet at participant's natural speed	
• Compare gait metrics collected between devices and APDM devices.	Tile and Carpet
Moving naturally between activities' stations	
• Compare gait metrics between devices and APDM devices, collected during the walk between the activities' stations and during the sit/stand position at the stations.	Walking pathway between activities' stations

Table 1. In-lab Assessments

Assessments	Objectives	Location
Free 10 minute walk (Cohort B)	
Compare gait metrics between devices and APDM devices, collected during the walk	10 minute walk outside the lab

1. At-home monitoring for approximately 2 weeks (from Day 1 to Day 15 + 3 days) during which participants will wear the devices under study. Complete a [daily activity diary](#) on Day 2 to Day 15 (Only Cohort A). Complete activity and sleep diary for Cohort B on Day 2 to day 15.
2. Cohort B Only: At-home monitoring day 7+2 Wearability/comfort questionnaire ([Annex 5](#)) for Panoramic Bracelet device and instruct participant to start wearing the GENEActiv device from Day 7 to end of study. Daily activity and sleep diary. ([Annex 8](#))
3. For Cohort A Only: A telephone follow-up interview at the end of the 2 weeks at-home monitoring period (Day 15 + 3 days) with administration of the [Wearability/comfort questionnaire \(Annex 5\)](#). For Cohort B follow up call to remind participants to take off devices and mail back. In addition to an end of study phone call for Cohort B.

For a detailed description of the study activities, see [Section 6 Schedule of Activities](#).

Inclusion Criteria

Participants must meet all of the following inclusion criteria to be eligible for inclusion in the study:

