10. Move naturally (sit/stand/walk) through a random path created by dice roll in the PflRe Lab (between activities' stations) while wearing device under study and APDM system as well as recorded with video/motion capture cameras. Participants will perform age-related activities using 6 activity stations for ~20 minutes (defined as follows: ~7 minutes of activities, ~5 minutes of break and ~7 minutes of activities). The task stations include 2 sitting activities (such as look through a book, draw/write), 2 standing activities (such as turn a switch or hang a coat), 2 walking activities (such as move blocks/objects, toss a beanbag and pick it up).
11. Free 10 minute walk outside the lab (Cohort B Only)
12. [Wearability/Comfort questionnaire \(Annex 5\)](#) followed by a [Cognitive Debrief](#) of the questionnaire.
13. Instruct participant and parent(s)/LAR on use of device under study and activity diary (Cohort A only) and activity and sleep diary (Cohort B only) at home.
14. Monitor for AEs.

[figure not shown]
A medically qualified individual is responsible for reviewing the inclusion/exclusion criteria, medical/surgical history, prior/concomitant treatments and for the review of the systems.

For the assessments 8, 9 and 10, every participant will have up to 3 attempts.

The in-lab gait and activity monitoring will be video recorded from multiple angles with multiple cameras (camera-based SIMI system). This will be used to provide gait speed and contextual information of each portion of the tasks and procedures that may be used by the reviewer when analyzing and interpreting the sensor data. Time segments of sensor data from each modality will be identified based on these annotations.

The locations of the device under study and the APDM system on the participant's body are defined on [Figure 1](#).

Figure 1. Wearable Sensor Device Locations on Participant In-lab Cohort A and B

Legend:

- Blue circle – APDM Opal sensors to be worn on each wrist, chest, lumbar, and above each shoe.
- Orange triangle – Device under study to be worn on nondominant wrist and lumbar.

All in-lab assessments will be performed at the PflRe lab with site personnel and will take approximately 2 hours.

Any event with a device, the impact of this event and the action taken with device will be recorded in a device assessment CRF during Visit 1.

At-home Monitoring (Day 1 to Day 15+3 days)

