### **2.2. Study Design**

*This is a non-randomized, single site, low-interventional study to compare gait quality metrics collected using the ActiGraph devices, APDM devices and GAITRite® walkway, during in-lab sessions (in the PfIRe Lab). There will be approximately 39 participants in Cohort A and 39 participants in Cohort B divided equally into 3 independent age groups based on the schematic detailed below:*

- *Group 1: 3 years to 5 years old inclusive;*
- *Group 2: 6 years to 11 years old inclusive;*
- *Group 3: 12 years to 17 years old inclusive.*

*Participant's assignment to a group will be determined by the age at the time the informed consent is signed. Participants will be recruited into age groups in parallel. Recruitment will stop in a group when there are at least 13 completers in that group. Participants who drop out for reasons other than safety before completion of the study may be replaced.*

*The study is composed of (see Figure 1):*

1. *A visit at the PfIRe Lab (Visit 1, Day 1), during which participant eligibility will be confirmed, consent and assent will be obtained. Participants will perform in-lab gait and activities monitoring procedures. During all these activities, participants will wear or interact with the following devices:*
  - a. *Wearable devices (ActiGraph for Cohort A), (Panoramic Bracelet device and GENEActiv for Cohort B);*
  - b. *GAITRite® Electronic Walkway;*

- c. *Ambulatory Parkinson's Disease Monitoring System (APDM);*
- d. *Camera based SIMI® system.*

*GAITRite® walkway, APDM will be used as reference comparators. For Cohort B of the protocol the aim is to use GENEActiv as a comparator device to Panoramic Bracelet during the at-home collection period. The in-lab gait and activity monitoring will be video recorded from multiple angles with multiple cameras (camera – based SIMI® system), this will be used to provide contextual information of each portion of the tasks and procedures that may be used by the reviewer when analyzing and interpreting the sensor data. As a tertiary/exploratory objective, gait speed recorded by the SIMI® system against the gait speed collected by GAITRite® walkway will be validated.*

The devices and activities in the study are listed in

Table 3 and

Table 3.

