### 6.5.2. To compare gait speed collected using the SIMI® system and GAITRite® walkway, during in-lab sessions.

Agreement between gait speed computed by GAITRite® (reference device) and SIMI® system (comparator device) will be assessed using the same methods described in Section 6.1.

Appropriate summaries and plots will be produced **per task** (colored by age group, if necessary) as follows:

- Scatter plots of gait speed from GAITRite® and SIMI® system with corresponding regression line and 95% CI will be plotted.
- Accuracy of SIMI®-derived gait speed will be determined by computing the mean difference, mean absolute difference, variation of the difference, the mean percent error, the mean absolute percent error and the effect size between the two devices.
- Bias will be assessed by Bland-Altman plots and 95% limits of agreement. Mean difference, lower and upper 95% limit of agreement will be computed.
- Intra-class correlation coefficient (ICC) and its lower and upper confidence limits between the two gait speeds will be computed.
- The correlation coefficients (Pearson's) between the two gait speed metrics will be calculated.
- Box and whisker plots of gait speed for the two devices will be generated.

- Mixed model regression analyses will be used to investigate the effect of device (e.g., GAITRite, SIMI), and interaction between device and task (normal/slow/fast walk tasks) on gait speed. The device, task, and their interaction will be fixed effects, and subject will be entered as random effect. Post-hoc t-tests might be performed between devices. Multiple comparisons, when necessary, will be performed using FDR. Age (or age group) and sex may be used as covariates in the models. The estimates for fixed effect parameters, standard errors, 95% CIs, and p-values, as well as the variance estimates for the random effect will be summarized. Results from all models will be presented in a table. Furthermore, Least Squares Means (LSMeans) together with their 95% CI will be calculated for each device-task combination (e.g. LSmean of GAITRite normal speed walk task).

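### In-lab text has SIMI gait speed compared with GAITRite without a cohort limit, but the objectives and SAP analyse it in Cohort A only; reconcile, and preferably add an exploratory Cohort B analysis

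*Protocol*

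**What the plan says.** Several places treat SIMI gait speed as a Visit 1 measurement without limiting it to a cohort:

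- Protocol, Study Design: the Visit 1 device list includes "Camera based SIMI system" with no cohort label, although the wearables in the same list are labelled by cohort.
- Protocol, Table 1: the walkway row has the purpose "Compare gait speed collected between SIMI system and GAITRite® walkway". That row carries no cohort label, while the free-walk row is marked for Cohort B.
- Protocol, Visit 1 (Day 1), on the video recording: "This will be used to provide gait speed and contextual information of each portion of the tasks and procedures".
- Protocol, Variables and Requirements: SIMI gait speed appears as a study variable and within a qualifying procedure, with no cohort limit on SIMI.

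The two documents differ on whether the comparison is definite. The protocol's Study Design section says "gait speed recorded by the SIMI system against the gait speed collected by GAITRite® walkway may be validated". SAP 2.2 says "gait speed recorded by the SIMI® system against the gait speed collected by GAITRite® walkway will be validated".

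The objective itself, "To compare gait speed collected using the SIMI system and GAITRite® walkway, during in-lab sessions", stands under Cohort A in the protocol Summary, in the objectives tables and in the Statistical Analysis section. The SAP follows this. The endpoint is in Table 6 (Cohort A), and 6.5.2, under the Cohort A exploratory objectives, says "Agreement between gait speed computed by GAITRite® (reference device) and SIMI® system (comparator device) will be assessed". The Cohort B objectives, SAP Table 7 and SAP 6.6 contain no SIMI item.

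**The concern.** A reader cannot tell whether Cohort B SIMI speeds are to be analysed. Children in both cohorts walk the same natural, slow and fast rounds on the walkway, and the general text has SIMI giving gait speed for all of them. Neither SIMI nor GAITRite depends on which wearable is under study, so the change of device between cohorts does not explain the restriction, and no other reason is given.

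What is at stake is modest: more precise agreement estimates for video gait speed, and a replication in a second group of children. Neither needs any extra procedure for a child.

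**Working it through.** **1. The passages side by side.** Protocol Study Design, Table 1, Variables, Visit 1 and Requirements, together with SAP 2.2, set no cohort limit on SIMI. The protocol Summary, objectives tables and Statistical Analysis section, together with SAP Table 6 and 6.5.2, give Cohort A only. The restriction therefore starts in the protocol's own objectives and the SAP carries it over. The mismatch lies between the general and the cohort-specific text, within each document.

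**2. The plan's own sample-size figure.** Study Size gives no figure for SIMI. For gait agreement it takes ICC 0.72 against a null of 0.27, one-sided alpha 0.05 and power 0.80, and states 17. The Walter-Eliasziw-Donner formula with k = 2 measurements is

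n = 1 + 2k(z_α + z_β)² / [(k − 1)(ln C)²], with C = (1 + kθ₀)/(1 + kθ₁) and θ = ICC/(1 − ICC).

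- θ₀ = 0.27/0.73 = 0.370 and θ₁ = 0.72/0.28 = 2.571.
- C = 1.740/6.143 = 0.283, so (ln C)² = 1.592.
- n = 1 + 4 × (1.645 + 0.842)²/1.592 = 16.54, rounded up to 17, which reproduces.
- 17/0.85 = 20, which also reproduces. The plan then roughly doubles this and sets 3 × 13 = 39.

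Cohort A alone therefore exceeds the number derived for gait validation.

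**3. Precision of the limits of agreement.** The inputs are n per cohort ("There will be approximately 39 participants in Cohort A and 39 participants in Cohort B") and the multiplier 1.96 from SAP 5.1. The SAP asks for the limits but not for intervals around them. The interval is used here to measure how well each limit is known. In units of the SD of the difference,

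half-width = t(0.975, n − 1) × √[1/n + 1.96²/(2(n − 1))].

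- n = 39: 2.024 × √(0.02564 + 0.05055) = 0.559.
- n = 78: 1.991 × √(0.01282 + 0.02495) = 0.387.
- Gain from adding Cohort B: 1 − 0.387/0.559 = 31% narrower.

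Other standard forms of the half-width (z for t, or 3/n or 2.92/n for the variance) give 29% to 31%. An exact noncentral-t interval has width 1.128 at n = 39 and 0.777 at n = 78, again 31% narrower.

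**4. Fewer usable Cohort B children.**

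| Usable in Cohort B | Cohort A interval wider than pooled by | Pooled interval narrower by |
|---|---|---|
| 39 | 44.4% | 1 − 1/1.444 = 31% |
| 33 | 38.5% | 1 − 1/1.385 = 28% |
| 30 | 35.4% | 1 − 1/1.354 = 26% |
| 20 | 24.8% | 1 − 1/1.248 = 20% |

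The calculation assumes one value per child per task, and one bias and one SD common to both cohorts.

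**The case against.** The strongest reply is that this is a scope choice. The protocol assigns the objective to Cohort A in three places and omits it from all three Cohort B lists. Its wording makes the validation optional, and the Cohort B video has another stated use, as context for interpreting sensor data. That stands. A reader might infer that the SAP dropped half the data for a protocol objective. The documents do not support this, because the objectives tables never gave Cohort B that objective.

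The general text is also imperfect evidence. The Visit 1 device list includes GENEActiv for Cohort B, although the Cohort B schedule first provides that device at Day 7+2. The Variables section likewise lists gait metrics from GENEActiv. This weakens those two passages. Table 1, the Visit 1 description and Requirements do not depend on them.

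Three further limits stand:

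- No requirement is missed. The objective is exploratory, has no precision target, and 39 exceeds the 17 to 20 derived for gait agreement.
- A reader might infer that agreement in the youngest children cannot be judged. SAP 6.5.2 works per task and plans no age-group limits, and neither document gives an acceptance limit, so that conclusion has no basis here.
- Comparability between cohorts is not established. Planned collection ran from April 2021 to April 2022 for Cohort A and from May to November 2023 for Cohort B. The documents do not say that the camera set-up stayed the same.

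**Conclusion.** The inconsistency is real and minor. General text in both documents has SIMI gait speed obtained and compared with GAITRite, while the objectives and the analysis confine the comparison to Cohort A without a reason. An optional validation in the protocol is also a definite one in the SAP. The consequence is that Cohort B speeds which the plan says will be produced are left unanalysed.

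Using them would narrow the 95% interval around each limit by about 31% at most, and by about 20% to 26% with 20 to 30 usable children, on the assumptions of equal bias and equal SD. It is tempting to turn the ratio round and say that the Cohort A limits of agreement are 44% less precise. That figure is the extra width of the interval around each limit under full Cohort B data. It does not mean that the limits are 44% wider, and they are not expected to move.

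**What to change.** First, state which cohorts the SIMI comparison covers and whether it is optional or definite. Then align protocol Table 1 and Study Design, the objectives, and SAP 2.2. If Cohort A only is intended, label the Table 1 row and SAP 2.2 accordingly and give the reason.

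Preferably, add the 6.5.2 analysis to SAP Table 7 and SAP 6.6 as an exploratory Cohort B analysis. Report each cohort separately first. Pool them, with cohort as a fixed factor, only if bias and SD are similar.

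Cost: the protocol's Data Analysis section lets the SAP modify planned analyses and reserves a protocol amendment for major changes to primary endpoints, so a SAP revision is enough for the analysis. Adding the item to the protocol's Cohort B objectives, or correcting the protocol text, would be a protocol change and could wait for the next amendment. SIMI speeds must be processed for up to 39 children with 3 rounds at each of 3 speeds, that is 39 × 9 = 351 walkway rounds. The camera set-up in the two collection periods must also be checked before pooling. No child undergoes an extra procedure.
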